## 1. SUMMARY OF THE RESEARCH

Title of the study	Single-center retrospective study on safety of total knee replacement surgery before and after the implementation of enhanced recovery program
Sponsor	Groupe Hospitalier de la Rochelle Ré Aunis
NCT number	NCT05028426
PI	[name]
Primary and secondary objectives	The objectives are to compare the number of adverse events at 1 month, the number of thromboembolic events, the average length of stay and the improvement of mobility before and after the implementation of rapid rehabilitation protocols after surgery
Methodology of reference (in France)	 MR-004  MR-005  MR-006
Data sources	 Medical records  Survey / Cohort / Register including data from the national health data system  Medicalization Program of Information Systems  Other source of Data
Study population	Patients over 18 years of age treated between 2015 and 2018 by the Orthopaedic Surgery and Traumatology Department of the Groupe Hospitalier de la Rochelle Ré Aunis for total knee replacement
Background	Enhanced Recovery After Surgery (ERAS) is a management method that aims to allow the patient to recover as quickly as possible their physical and mental capacities. It was initially developed for colon surgery and has recently been extended to orthopaedic surgery protocols.
Contexte of the study	This innovative method has been practiced by the Orthopaedic Surgery and Traumatology Department of the La Rochelle Ré Aunis Hospital Group since January 2017.
Methodology	Single center retrospective study
Statistical analysis plan	
Epidemiological analysis :
 
 
- Description of Patients classified into three groups according to the type of care management they received: traditional care, some elements of a fast-track program during a transition period, and full enhanced recovery program.
 
- Using means +/- standard deviations, counts, and percentages to describe continuous and categorical variables, respectively
 
 
Comparative analysis of the three groups :
 
 
- Normal distributions will be verified and T-test or Mann-Whitney tests will be used to compare continuous data of independent samples where appropriate.
 
- Chi-square test of homogeneity will be used for categorical variables.
 
- An alpha level of 0.05 will be used for all statistical tests.
 

Justification of the public interest character of the study	Evaluation of the effectiveness and safety of a recent management protocol
Timetable for the study and provisional schedule for communicating the results	September 2019: drafting of the information leaflet, the protocol and the CRF From October 2019 to June 2020 : data collection End of 2020 : exploitation of the results and writing of a report/scientific manuscript

## **2. SCIENTIFIC JUSTIFICATION**

Enhanced recovery programs are an organizational evolution in surgical patient management, in which the patient becomes an actor of his or her own recovery. This multimodal approach aims at optimizing patient physiological and psychological states across preoperative, intraoperative and postoperative domains of care. First described by Kehlet[1], these programs have been gradually modified and used for many surgery specialties, including the perioperative management of hip and knee replacements[2]. Convincing results for the benefit of the patients have been achieved in the reduction of perioperative complications, shorter hospital stays, and some improvements in quality of life (rapid restoration of physical and mental capacities)[3]. These programs also contributes to optimizing the production of care in light of human and material constraints, as they participate in 1) limiting the presence of patients in hospital by reducing the length of stay ; 2) a better control of the organization, with a better responsiveness to new challenges, like infection ; and 3) possible increase in the number of patients treated, which will be necessary according to various projections[4, 5].

Despite the proven benefits and numerous publications on enhanced recovery programs for total knee arthroplasty, physicians are still faced with the knowing-doing gap of translating the scientific data into daily clinical practice[6, 7].

In our center, the decision to take the step happened at the end of 2016. It was proposed by a young surgeon that have been trained on this new approach during his studies and who convinced the head of the surgery department of the benefits for the patients, the healthcare workers, and the institution. The transition took place in two stages, first operative and postoperative techniques were modified, and then preoperative education and counselling were added. Our hypothesis was that the shift from a traditional method of care to an enhanced recovery program can be implemented in a secondary-care hospital while ensuring the same safety and effectiveness for patients.

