## **3. OBJECTIVES**

### **3.1. Main objective**

The main objective is to measure early complication rate after total knee arthroplasty.

It will be determined by the number of patients with complication detected within 3 months after surgery.

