## 8.2. Statistical methods employed

Patients will be classified into three groups according to the type of care management they received: Phase 1, 2 or 3.

Means +/- standard deviations, counts, and percentages will be used to describe continuous and categorical variables, respectively.

Normal distributions will be verified and T-test or Mann-Whitney tests will be used to compare continuous data of independent samples where appropriate.

Chi-square test of homogeneity will be for categorical variables.

An alpha level of 0.05 will define statistical significance.

XLSTAT (Addinsoft) will be used for statistical analysis.

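### The hypothesis is unchanged safety and effectiveness, but the plan has only tests of no difference at 0.05 and no confidence interval for a between-phase difference, so a non-significant result could not support it

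*Combined protocol and SAP*

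**What the plan says.** Section 2 states the study's one hypothesis: that the move from traditional care to enhanced recovery "can be implemented in a secondary-care hospital while ensuring the same safety and effectiveness for patients". The objectives row of the summary (section 1) speaks of comparing outcomes "before and after the implementation of rapid rehabilitation protocols after surgery". Section 3.1 is worded descriptively: "The main objective is to measure early complication rate after total knee arthroplasty".

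The analysis is set out in the summary's statistical analysis plan row and in section 8.2.

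- Description: "Means +/- standard deviations, counts, and percentages will be used to describe continuous and categorical variables, respectively".
- Inference: under the summary's item "Comparative analysis of the three groups", continuous outcomes get a t-test or Mann-Whitney test. For the rest, section 8.2 says "Chi-square test of homogeneity will be for categorical variables".
- Threshold: "An alpha level of 0.05 will be used for all statistical tests" in the summary, and "An alpha level of 0.05 will define statistical significance" in section 8.2.

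Neither place plans an estimate of a between-phase difference, a confidence interval, a margin, or a rule for reading a non-significant result. Section 8.1 gives a hospital count of 470 patients, with no power or precision.

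**The concern.** The planned tests all take equality as the null hypothesis. Rejecting it is evidence of a difference; failing to reject it is not evidence of equality. The sponsor's hypothesis, though, is that safety and effectiveness are maintained. If that is true, the tests will usually be non-significant, which is the one outcome the plan gives no means to interpret. Only a significant result favouring the programme could support no loss of safety, and only for the outcome tested.

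What is at stake is the study's main message. A report limited to the planned analysis could say that complications did not differ significantly, without showing how large an increase remains compatible with the data. The document does not say that non-significance will be read as sameness. It is silent on the reading, and its hypothesis invites that one.

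**Working it through.** The plan has no power, margin or precision figure to reproduce. The central point is logical and needs no arithmetic. The figures below show only its possible size.

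**Inputs**

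- From the document: 470 patients (section 8.1); surgery from January 2015 to December 2018, i.e. 48 months (section 5.1); Phase 2 changes by the end of 2016 and Phase 3 from 2018 (section 6); alpha 0.05 (section 8.2).
- Assumed: even accrual, with Phase 1 = 24 months, Phase 2 = 12 and Phase 3 = 12. Then 470 × 24/48 = 235 and 470 × 12/48 = 117.5, giving 235/118/117. Before vs after is then 235 vs 118 + 117 = 235.
- Assumed: Phase 1 complication rates of 2%, 5%, 10% and 15%, since the document gives none. Tests are two-sided and chi-square is uncorrected.

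**Step 1. What a non-significant result can hide (hypothetical counts)**

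The interval is Newcombe's, built from the Wilson limits (l, u) of each proportion. With d = p3 − p1:

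- lower limit = d − √[(p3 − l3)² + (u1 − p1)²]
- upper limit = d + √[(u3 − p3)² + (p1 − l1)²]

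For 12/235 vs 12/117: p1 = 5.11% (Wilson 2.94 to 8.71), p3 = 10.26% (5.96 to 17.07), d = 5.15.

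- Lower = 5.15 − √(4.29² + 3.61²) = −0.5
- Upper = 5.15 + √(6.82² + 2.16²) = +12.3

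| Hypothetical result | p | Difference, points | 95% CI |
|---|---|---|---|
| Phase 1 12/235, Phase 3 12/117 | 0.07 | +5.2 | −0.5 to +12.3 |
| Before 12/235, after 18/235 | 0.26 | +2.6 | −2.0 to +7.2 |
| Phase 1 12/235, Phase 3 6/117 | 0.99 | 0.0 | −4.5 to +6.0 |
| Phase 1 24/235, Phase 3 4/117 | 0.03 | −6.8 | −11.8 to −0.8 |

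The three-group test on 12/235, 6/118 and 12/117 gives chi-square 3.91 on 2 df, p = 0.14. The first three rows would all be reported as not significant, yet they say quite different things about safety. The last row is the favourable case that would support no loss of safety for that outcome.

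**Step 2. How often a true rise would be missed**

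Two-group power is by exact binomial enumeration. Three-group power is by simulation (400,000 tables per scenario), with only Phase 3 worse.

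| Test | True rise | 2% | 5% | 10% | 15% |
|---|---|---|---|---|---|
| Phase 3 vs Phase 1 | 5 points | 63% | 43% | 29% | 23% |
| Phase 3 vs Phase 1 | 10 points | 97% | 88% | 73% | 62% |
| Before vs after | 5 points | 77% | 54% | 38% | 30% |
| Before vs after | 10 points | >99% | 96% | 87% | 78% |
| Three groups | 5 points | 62% | 38% | 25% | 19% |
| Three groups | 10 points | 97% | 86% | 69% | 58% |

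Columns are Phase 1 rates. Section 8.1 does not say that 470 is net of the eligibility criteria in sections 5.1 and 5.2. If 400 were analysable (200 vs 100), power for a 5-point rise, Phase 3 vs Phase 1, would be 57%, 38%, 26% and 20%.

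**Step 3. Precision the plan could report**

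Half-width = 1.96 √[p(1 − p)(1/na + 1/nb)] at equal true rates. At 10% with 235 and 117: 1.96 × √[0.09 × (1/235 + 1/117)] = 6.7 points. Across 2%, 5%, 10% and 15%:

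- Phase 3 minus Phase 1: 3.1, 4.8, 6.7 and 7.9 points
- After minus before: 2.5, 3.9, 5.4 and 6.5 points

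**The case against.** The strongest reply is that the plan never draws the faulty inference. The hypothesis is one past-tense sentence in the background, section 3 only sets out to measure rates, and counts by group will be reported, so a reader can derive the interval. Part of this stands: the defect is an omission, not a stated error. It does not dispose of the point, because the summary sets out to compare and plans a comparative analysis, and the hypothesis is the only one given. Readers could rebuild the interval for proportions, but not the shift behind a Mann-Whitney test, which needs patient-level data.

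A second reply is that the mismatch is sharpest for complications. For length of stay and mobility, where the document anticipates improvement, a test of difference is a reasonable tool. That is fair as to emphasis, although the hypothesis also covers effectiveness.

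Third, the rates and phase sizes are assumed, and the protocol's before-after contrast has better power than Phase 3 vs Phase 1. Both are true, and both contrasts are shown above. A 5-point rise would still often be missed at base rates of 5% or more.

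Finally, an unadjusted interval between calendar periods reflects sampling error only. That is a limit on how the interval should be read, and it applies equally to the planned p-values.

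**Conclusion.** The concern holds and should be fixed. As written, the planned inference cannot support the stated hypothesis if the tests are non-significant, and this does not depend on any assumed figure.

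The size does. With 470 patients split 235/118/117 and base rates of 2% to 15%, a 10-point rise would usually be detected (62% to 97% for Phase 3 vs Phase 1). A 5-point rise often would not be (63% down to 23%; 77% down to 30% for before vs after). Fewer analysable patients would lower these figures. The data remain usable; it is the stated analysis and its reading that need changing.

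**What to change.** In section 8.2 and the matching row of the summary:

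1. Name one contrast before analysis: Phase 3 vs Phase 1, or before vs after as in the summary's objectives. For it, report the difference in the proportion of patients with an early complication, with a two-sided 95% CI (Newcombe or Miettinen-Nurminen). Do the same for late complications. For length of stay and knee motion, report a difference in means with 95% CI, or a Hodges-Lehmann shift with 95% CI where Mann-Whitney is used.
2. State that p > 0.05 will not be read as the same safety. Base the conclusion on the estimate and on the largest excess that the interval does not exclude, noting that the interval covers sampling error only.

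Both items are wording. They need no new patients or variables, and the Hodges-Lehmann interval uses patient-level data already collected. The downside is that the interval may be wide and the conclusion less favourable than a bare statement of no significant difference.

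A margin is optional. It is needed only if the sponsor wants a formal conclusion of the same safety. It would have to be clinically justified before the data are seen, and the document does not show whether that is still possible.

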## **3. OBJECTIVES**

### **3.1. Main objective**

The main objective is to measure early complication rate after total knee arthroplasty.

It will be determined by the number of patients with complication detected within 3 months after surgery.

### **3.2. Secondary objectives**

Secondary objectives are to measure:

- Late complication rate (within 2 years after surgery)
- Length of Hospital Stay
- Preoperative Knee Extension
- Postoperative Knee Extension
- Preoperative Knee Flexion
- Postoperative Knee Flexion

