### **5.3. Feasibility and recruitment procedures**

Perioperative arthroplasty data will be collected from medical records.

Five orthopedic surgeons performed total knee replacements.

The inclusion period last from January 2015 to December 2018.

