## **Phase 3**

To complete this program, from 2018 onwards, educational therapy with a nurse has been added. Patients were more comprehensively informed about the global care pathway. If necessary, counselling to assist with smoking cessation and addiction[15] could be offered in order to reduce risk of postoperative complications. Nutritional care could be set up on demand. If patients wished to be discharged to a rehabilitation center, the demand for beds was anticipated in order to reduce hospital waiting times. Operative and post-operative management was the same as before, except that draining was not systematic as it has not been used in well-documented hip and knee enhanced recovery programs, with no increase in complications[11].

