## **8. STATISTICAL ASPECTS**

### **8.1. Calculation of study size**

According to the hospital information system, 470 patients were taken care for total knee arthroplasty surgery over the study period.

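### The scheduled record review ends before about half of the 2018 (Phase 3) patients can reach 2 years, so late complications are under-counted almost only in the full-programme group

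*Combined protocol and SAP*

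**What the plan says.** - Section 3.2 lists "Late complication rate (within 2 years after surgery") as a secondary outcome.
- Section 5.3: "The inclusion period last from January 2015 to December 2018". Sections 5.1 and 7.1 give the same range.
- Section 6, Phase 3: "from 2018 onwards, educational therapy with a nurse has been added". Phase 3 is therefore the 2018 cohort. Phase 2 began at the end of 2016, so it is essentially the 2017 cohort.
- Section 1, timetable: "From October 2019 to June 2020 : data collection", then "End of 2020 : exploitation of the results and writing of a report/scientific manuscript". No further collection is listed.
- Section 8.2 groups patients by phase and states: "Chi-square test of homogeneity will be for categorical variables". It gives no time-to-event method, minimum follow-up, data cut-off or censoring rule. The summary in section 1 gives none either.
- Section 8.1 reports that "470 patients were taken care for total knee arthroplasty surgery over the study period", with no split by phase.
- The main outcome in section 3.1 is "the number of patients with complication detected within 3 months after surgery".

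**The concern.** A patient operated on in December 2018 has not completed 2 years until December 2020, six months after the last scheduled day of record collection. A chi-square on simple proportions, with everyone in the denominator, counts unobserved months as free of complications. Nothing in the data would reveal this, because the record shows no missing value.

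The shortfall is not shared equally. Calendar time defines the phases, so the most recent phase has the shortest follow-up, and that phase is the full programme. With no true difference, its late rate would be reported too low.

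The study's hypothesis (section 2) is that safety is maintained, so the more serious risk is that a real excess is hidden. Late complications are also the only listed safety outcome beyond 3 months.

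**Working it through.** The plan has no follow-up or power calculation to reproduce, so the check is calendar arithmetic followed by an illustration.

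**Inputs from the plan.** Window of 24 months; surgery from January 2015 to December 2018; Phase 3 = 2018; review between 1 October 2019 and 30 June 2020; 470 patients.

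**Assumptions.** Phase 1 = 2015–16 and Phase 2 = 2017; even accrual within each phase; reading date unrelated to surgery date unless stated.

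**Step 1: follow-up at review** (review date minus surgery date).
- Phase 1: at least 33 months (end of December 2016 to 1 October 2019).
- Phase 2: at least 21 months. It falls short of 24 only for late-2017 patients read before the end of December 2019.
- Phase 3: 9 months (end of December 2018 to 1 October 2019) to 30 months (January 2018 to 30 June 2020).

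**Step 2: share with a full 24 months.**

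| Records read | Phase 1 | Phase 2 | Phase 3 |
|---|---|---|---|
| All on 30 June 2020 | 100% | 100% | 50% |
| Spread evenly over the period | 100% | 96% | 17% |
| All on 1 October 2019 | 100% | 75% | 0% |

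For the first row, surgeries after 30 June 2018 are short: 184 of 365 days = 50.4%. At 470/4 = 117.5 patients a year, that is about 59 patients. For the second row, count months from 1 January 2018. Review R is uniform on 21 to 30, and a patient is complete if surgery falls before R − 24. The share is (1/9) × ∫₀⁶ (x/12) dx = (1/9) × 1.5 = 1/6, or 17%.

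Phase 3 holds 96% to 100% of all the missing person-time, depending on the reading date.

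**Step 3: effect on the reported rate.** Assume the same true 2-year risk p in every phase and a constant hazard h = −ln(1 − p)/24 per month. The observed risk is the mean of 1 − exp(−h × min(follow-up, 24)). For p = 10%, h = 0.00439:
- 30 June 2020: half of Phase 3 is complete and half has 18 to 24 months (mean 21). 0.5 × 10% + 0.5 × (1 − e^(−0.00439 × 21)) = 5.0% + 0.5 × 8.8% = 9.4%.
- 1 October 2019: follow-up is 9 to 21 months (mean 15). 1 − e^(−0.00439 × 15) ≈ 6.4%.
- Even spread: about 8.0%, by simulation.

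| True risk in all phases | 30 June 2020 | Even spread | 1 October 2019 |
|---|---|---|---|
| 5% | 4.7% | 4.0% | 3.2% |
| 10% | 9.4% | 8.0% | 6.4% |
| 15% | 14.1% | 12.1% | 9.6% |
| 10%, half of it in months 0–3 | 9.6% | 8.9% | 7.9% |

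Phase 1 shows the true risk throughout.

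**Step 4: events and test error.** Take a 235/117/118 split of the 470 (even accrual, assumed). At 10% risk Phase 3 should have about 118 × 0.10 ≈ 12 events. It misses about 0.7, 2.3 or 4.3 of them in the three scenarios. The three-group chi-square at 0.05 then rejects, with no true difference, in 5.0%, 7.1% or 15.0% of simulated studies. Across true risks of 5% to 15% the ranges are 4.7–5.2%, 5.5–9.1% and 8.3–22.5%.

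**Control.** With review on 31 December 2020 every patient is complete and rejection is 4.8–5.0% over the same risks, apart from simulation error.

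**The case against.** **The timetable may be out of date.** It appears only in the summary, whose outcomes differ from those in section 3. It dates drafting to September 2019, although the reference list contains 2020 publications. Its heading also calls at least part of it provisional. Collection may well have run later. This stands as a limit on what was actually done, but the documents plan no later date.

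**The plan does not say that incomplete patients count as event-free.** Correct: restricting to patients with 24 months would also fit the text. But no restriction is stated, and a simple proportion of all patients in each group is the natural reading.

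**Groups are defined by care received, not by date.** If some 2018 patients did not receive the full programme, part of the shortfall moves to Phase 2 and the Phase 2 figures above change. Section 6 nevertheless dates Phase 3 from 2018.

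**The size may be small.** This has the most force. Reading about 470 charts on the first day is only a theoretical bound. If charts are read in order of surgery date, 61.9% of Phase 3 is incomplete, but it would still show about 9.3% against 10%, with test error close to 5%. Only even or early reading of the 2018 records makes the bias material.

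**Calendar follow-up is not observed follow-up.** Single-centre records may miss complications treated elsewhere, in any phase. This is a separate weakness and does not offset the difference between phases.

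**Conclusion.** The concern holds. Under the only collection period stated, no patient operated on after June 2018 can have a full 2-year window. Phase 3 is at least about half incomplete while Phase 1 is complete and Phase 2 nearly so. The crude late-complication comparison is therefore biased towards the full programme.

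The relative shortfall in the Phase 3 rate, under constant hazard, is about 6% with reading at the end of June 2020 (9.4% against 10%), about 20% with evenly spread reading, and about 36% at the October 2019 bound. At the June cut-off the rate is slightly low and the test's error rate is unchanged. A real excess could also be masked: a true 15% in Phase 3 would appear as 12.1% with even reading.

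These sizes rest on even accrual, Phase 3 being calendar 2018, the timetable being followed, and the assumed risks and hazard shapes. The existence and direction of the bias rest on the plan's own dates and on counting every patient in the denominator. One secondary outcome is affected. The main outcome is not, since the shortest follow-up is 9 months. This should be fixed, but it does not threaten the main objective.

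**What to change.** State one of the following in sections 7.1 and 8.2.

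1. **Complete the window.** Finish the late-complication review after 31 December 2020, re-reading all 2018 records and any late-2017 record read before its 24-month date. Cost: about 6 months' delay for this one outcome.
2. **Shorten the window.** Keep the timetable, re-read all 2018 records at 30 June 2020, and compare all phases over a common 18 months. With phases split by calendar year, Phases 1 and 2 need no re-reading, since their minimum follow-up is 33 and 21 months. Cost: an 18-month rather than a 24-month outcome.
3. **Model the follow-up.** Record each patient's review date and compare Kaplan-Meier curves (log-rank), censoring administratively at that date or 24 months, whichever is earlier, and not at last contact. Report at a time every phase reaches, because a Phase 3 record read on 1 October 2019 has at most 21 months. Cost: one date field and SAP wording. This option assumes the records capture complications up to the review date, which should be stated.

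Options 1 and 2 avoid the censoring question and are the simpler choices. If collection in fact ran past December 2020, stating that cut-off date, and that the late-complication records were read or re-read then, is enough.

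### Postoperative knee flexion and extension are compared across sequential phases with no stated measurement time and without using the collected preoperative values

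*Combined protocol and SAP*

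**What the plan says.** Section 3.2 names "Postoperative Knee Extension" and "Postoperative Knee Flexion", and lists the two preoperative measurements as separate items. None of the four carries a time point. Other outcomes do have one: the main outcome in section 3.1 is the "number of patients with complication detected within 3 months after surgery", and section 3.2 gives late complications a 2-year limit.

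The Summary (section 1) sets out to compare "the average length of stay and the improvement of mobility before and after the implementation of rapid rehabilitation protocols after surgery". Before and after here refer to the introduction of the programme, not to the operation. The notion of improvement nevertheless implies a change from the patient's own preoperative state. The 1-month horizon in the same sentence belongs to adverse events, not to mobility.

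Section 8.2 classifies patients by phase and states that "T-test or Mann-Whitney tests will be used to compare continuous data of independent samples". It mentions no change score, covariate or adjustment for days since surgery. On sources, section 5.3 says "Perioperative arthroplasty data will be collected from medical records", and the Summary ticks medical records in general.

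**The concern.** The phases follow one another in calendar time and patients were not randomised to them. Two things can then move the postoperative reading apart from the programme itself.

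The first is the patient's preoperative motion. If the case mix changed between 2015 and 2018, the phases may start from different values, and a test on the postoperative value alone carries that difference forward. The plan collects the variable that would remove most of this and does not say that it will be used.

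The second is the day of measurement. In a retrospective chart study the day is whatever was recorded. If knee motion is still recovering when it is read and the typical reading day differs by phase, the comparison partly measures time since surgery. With no rule, extractors may also choose differently among several charted values.

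At stake is the mobility objective, which bears on the effectiveness half of the hypothesis in section 2. The main outcome is not affected.

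**Working it through.** **Step 1. Search for a measurement time.** The Summary, sections 3.1, 3.2, 5.3, 6, 7.1 and 8.2 were read for a day, visit or window attached to knee motion. None was found. Complications have 3 months (3.1) and 2 years (3.2).

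**Step 2. What each analysis estimates.** Let D be the difference between two phases in mean preoperative motion, and b the slope of postoperative on preoperative motion. Let T be the difference in mean measurement day, and g the gain per day around that time. With a programme effect E, the expected difference is:

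- postoperative value, unadjusted: E + bD + gT
- change score, unadjusted: E + (b − 1)D + gT
- postoperative value adjusted for preoperative value: E + gT, if the relation is linear
- the same, with one common measurement time: E

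The tests in section 8.2, applied to the outcomes as listed in section 3.2, give the first line. The documents give no value for D, b, g or T.

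**Step 3. Illustration of the timing term only.** The plan states no power or SD, so there is no figure to reproduce. From the documents: 470 patients (8.1) and alpha 0.05 (8.2), taken as two-sided. Assumed:

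- phase sizes proportional to calendar time over 48 months: 470 × 24/48 = 235 for 2015–16, and 470 × 12/48 = 117.5 for each of 2017 and 2018, taken as 118 and 117
- SD of flexion 10, 15 or 20 degrees
- gain of 1 to 3 degrees per day
- reading 1 to 3 days earlier in Phase 3

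The timing shift is gain per day × days earlier, so it runs from 1 × 1 = 1 to 3 × 3 = 9 degrees.

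SE = SD × √(1/235 + 1/117) = SD × 0.1131. The chance of a significant result with no true effect is Φ(shift/SE − 1.96) + Φ(−shift/SE − 1.96).

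| SD | SE | 1.96 × SE | shift 2 | shift 4 | shift 6 | shift for 80% |
|---|---|---|---|---|---|---|
| 10 | 1.13 | 2.2 | 42% | 94% | 100% | 3.2 |
| 15 | 1.70 | 3.3 | 22% | 65% | 94% | 4.8 |
| 20 | 2.26 | 4.4 | 14% | 42% | 76% | 6.3 |

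A true shift equal to 1.96 × SE is significant only about half the time; it is not a threshold above which significance is assured. If the measurement day does not depend on phase, the shift is 0 and the rate stays at 5%.

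**The case against.** A reader might infer that motion was read during the stay, so that earlier discharge under the programme produces a mobility difference by itself. The documents do not support that. The word perioperative in section 5.3 is the only hint. The Summary's source is medical records in general, and outcomes at 3 months and 2 years imply that later records are used. If motion came from a clinic visit, earlier discharge would not itself cause the bias, although unequal visit timing still could.

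Nor do the phases differ in time to discharge by definition. Section 6 sets no discharge target for any phase. Section 2 describes shorter stay as a benefit of such programmes generally. The Phase 3 step of requesting rehabilitation beds early concerns patients who wish to go there. Shorter stay is expected, and it is an outcome, but it is not a fixed contrast.

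A reader might also infer that the mobility results can support no conclusion in either direction. That too goes beyond the documents. If later phases were read earlier while motion was still improving, the timing term would run against the programme. Equal or better motion in those phases would then be conservative with respect to timing. The preoperative difference, by contrast, could run either way.

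Finally, section 8.2 does not exclude a change score. That is true, but none is specified, section 3.2 lists the values separately, and a change score still leaves (b − 1)D.

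Two facts survive all of this: no measurement time is given, and no analysis is stated that uses the preoperative value.

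**Conclusion.** The point holds in this form: the postoperative motion outcomes have no defined time, and the stated comparison is unadjusted although the baseline is collected and improvement is the stated objective. A phase difference can therefore reflect preoperative motion. It can reflect time since surgery only if the charted measurement day differs by phase, which the documents neither show nor rule out.

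The size cannot be derived from the plan. The percentages above rest on assumed SDs, recovery rates, timing differences and phase sizes. They show only that, with about 470 patients, a shift of a few degrees would be enough to matter. The weakness concerns secondary outcomes and is inexpensive to correct.

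**What to change.** In section 8.2, analyse postoperative flexion and postoperative extension each by linear regression on phase (three levels), adjusted for the corresponding preoperative value. The data are already to be collected, so this costs only wording.

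In section 3.2, define the postoperative value as the one nearest a single stated time point within a stated window, the same for all phases. The documents describe no visit at which motion was measured, so the sponsor should choose the time point from what the charts contain, before comparing values by phase. Record the measurement date at extraction and add days since surgery to the regression. Report by phase the days from surgery to measurement and the number of patients without an in-window value.

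The costs are real but small. The Summary schedules collection from October 2019 to June 2020, so obtaining dates may mean reopening some charts. Patients without an in-window value drop out of these two analyses. That loss may differ by phase and so introduce its own selection, which is why the counts should be reported.
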